7. STUDY DESIGN

I) Primary and Secondary Variables

Primary Outcome Variable:

Clinical and endoscopic remission, steroid-free at 8 and 54 weeks, without rescue treatment and without the need for steroids up to week 54.

Secondary Variables (Variables of Interest):

- **Clinical Remission** (assessed at weeks 8 and 54): Mayo Score \leq 2 points with no individual variable $>$ 1.
- **Endoscopic Remission**: Mayo endoscopic subscore of 0 or 1.
- **Clinical Response** (assessed at weeks 8 and 54): a reduction in the Mayo score by at least 3 points and at least 30%, with a decrease in the rectal bleeding subscore of at least 1 point or to an absolute value of 0 or 1.
- **Early Clinical Response**: a decrease in the clinical Mayo subscore by at least 3 points and at least 30%, with a decrease in the rectal bleeding subscore of at least 1 point or to an absolute value of 0 or 1, at days 3 and 7 of corticosteroid treatment.
- **Relapse**: reappearance of symptoms, defined as a Mayo clinical subscore $>$ 2. The time of relapse from treatment initiation will be recorded.
- **Corticosteroid Dependency**: relapse during prednisone tapering or within three months after corticosteroid discontinuation.
- **Rescue Treatment**: restart or increase of the established corticosteroid dose (including topically acting oral corticosteroids) or initiation of any treatment for ulcerative colitis other than mesalazine, including biological agents (infliximab, adalimumab, golimumab, vedolizumab), calcineurin inhibitors (cyclosporine, tacrolimus), thiopurines (azathioprine, mercaptopurine), methotrexate, leukapheresis, or colectomy.
- **Need for Surgery** and time to surgery from treatment initiation.
- **Adverse Event Rate** and rate of severe adverse events (including hospitalizations) recorded throughout the study duration.
- **Fecal Calprotectin Determination**.

II) Study Design

This is a Phase IV, controlled, prospective, randomized, open, multicenter study to compare two corticosteroid treatment regimens for moderate UC flares.

III) Estimated Number of Subjects, Sample Size, and Justification

Study Subjects: Adult patients of both sexes with active moderate ulcerative colitis, with or without maintenance treatment or with oral/topical mesalazine.

Sample Size: 148 patients.

Sample Size Calculation:

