Assuming a probability of clinical and endoscopic remission at 8 weeks and sustained without corticosteroid reintroduction or rescue treatment at 54 weeks of 20% in the control group (oral prednisone), a total of 148 patients are needed to detect a $\geq 20\%$ improvement in the therapeutic group (one-tailed test) with a significance level (α) of 0.05 and a power (β) of 0.20, accounting for an estimated 10% dropout rate.

IV) Randomization and Blinding Techniques

After the patient signs the informed consent document approved by the Research Ethics Committee and AEMPS, and meets all inclusion criteria and none of the exclusion criteria, they will be eligible for inclusion in the trial. Patients will be randomized (1:1) into each treatment arm via a computerized system provided by AEG-RedCap. Randomization will be performed in blocks of 4 and stratified by (1) whether the disease is newly diagnosed, and (2) whether the patient has received maintenance treatment with mesalazine at doses > 2 grams/day in the last three months.

This is an open-label study, meaning both the study subjects and investigators will be aware of the assigned treatment. However, blinding will be maintained in the analysis of blood samples for corticosteroid response predictive factors and calprotectin levels in fecal samples, which will be centralized and blinded. The technician conducting the measurement will not know the treatment arm or the clinical response associated with each sample.

V) Treatment Description

The study medication (methylprednisolone for intravenous bolus) will be supplied by the sponsor, while the oral prednisone, calcium supplements, and aminosalicylates will be supplied as per routine clinical practice.

Treatment Groups:

1. **Intravenous Bolus Group:** 0.5 g/day of methylprednisolone administered intravenously for 3 consecutive days, followed by oral prednisone 60 mg/day for 1 week, with a subsequent tapering regimen (decrease by 10 mg weekly until 20 mg, followed by a decrease of 5 mg weekly until complete withdrawal).
2. **Oral Prednisone Group:** 60 mg/day for 1 week, followed by a tapering regimen (decrease by 10 mg weekly until 20 mg, followed by a decrease of 5 mg weekly until complete withdrawal).

In both groups:

- **Concomitant 5-ASA Suppository Treatment:** 1g/day during the first 4 weeks.
- **Calcium and Vitamin D Supplementation:** Calcium 1000 mg/day and Vitamin D 800 IU/day until corticosteroid withdrawal.

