- **Maintenance Mesalazine Treatment:** Mesalazine 2-2.4 g/day starting from prednisone tapering to 20 mg/day (in patients receiving 5-ASA during the flare-up, it will be discontinued upon inclusion in the study).

- Any other concomitant treatment received by the patient during the study must be recorded in the e-CRD.

Study Procedures: (summarized in Annex 8)

1. Inclusion and exclusion criteria will be reviewed, and informed consent will be signed at Visit 0.
2. Pre-inclusion epidemiological and clinical data will be collected.
3. Anthropometric data: height and weight, taken at the screening visit (V0).
4. Stool sample collection (Clostridium Difficile toxin determination and coproculture) and pregnancy test for women at the screening visit (V0).
5. Vital signs (temperature, heart rate, and blood pressure) and basic physical examination at each visit (V0 to V8).
6. Disease Activity Index according to the Mayo Clinic score (Disease Activity Index – DAI, Annex 2) will be calculated at visits V1, V5, and V8, and clinical subscore will be calculated at all other study visits. Walmsley Index will be calculated at all visits (Annex 3).
7. General laboratory tests (including blood count, renal and liver function, and C-reactive protein) and fecal sample collection for fecal calprotectin determination (samples preserved frozen until study completion for centralized analysis) at each visit.
8. Blood sample collection at baseline for corticosteroid response predictive factors analysis.
9. Rectosigmoidoscopy and Mayo endoscopic subscore calculation (Annex 2) at Visits V0 or V1, V5, and V8.
10. Clinical response assessment at Visits V2 and V3; clinical and endoscopic response assessment at Visits V5 and V8.
11. **Extra Visit for Intravenous Bolus Group (Group 1):** an additional visit on Day 2 (Visit 1.1) for administration of the second corticosteroid bolus.

VI) Recruitment Period, Follow-Up, and Study Duration

- **Patient Inclusion Start Date:** September 2018
- **Patient Inclusion End Date:** September 2020
- **Recruitment Period:** 104 weeks
- **Patient Treatment Duration:** 8 weeks
- **Patient Follow-Up Duration:** 42 weeks
- **Expected Completion Date for Last Enrolled Patient:** September 2021
- **Total Study Duration:** 156 weeks
- **Duration of Patient Participation:** 12 months

VII) Criteria for Premature Study Termination and Interruption

Criteria for Premature Study Termination:

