- **Patient Decision:** Patients may withdraw from the study at any time without any penalty or impact on their disease management or subsequent required treatments.
- **Serious Complications Due to Steroid Treatment:** Occurrence of severe adverse events related to corticosteroid treatment.

- **Lack of Early Clinical Response.**
- **Lack of Clinical and Endoscopic Remission, Steroid-Free at Week 8.**
- **Clinical Worsening and Need for Rescue Treatment or Serious Adverse Event:** At the investigator's discretion, this can occur at any time during the study.

VIII) Procedures to Verify Adherence to Oral Treatment

This procedure is intended to determine the study medication adherence of the subjects. The principal investigator or a delegated person will provide detailed instructions to the patient regarding medication intake, along with an informative medication diary to be returned upon treatment completion (see Annex 6). Therefore, the principal investigator or delegated personnel must maintain product traceability and record medication administration per patient visit in the electronic case report form (e-CRD). Any medication-related incidents must be documented in the patient's clinical history and recorded in the e-CRF.

IX) Blinding Techniques

This is an open-label study, meaning no blinding will be applied except for the analysis of blood samples for predictive factors of corticosteroid response and the determination of fecal calprotectin in collected fecal samples. These analyses will be conducted centrally and blinded to ensure the laboratory technician performing the analysis is unaware of the treatment group and the patient's clinical response.

Evaluation of the primary outcome variable will be performed by the endoscopy services of the participating hospitals. Endoscopists will conduct a blinded assessment of endoscopic procedures (third-party blinded evaluations).

X) Data Identification

Investigators will comply with GCP standards. All information collected during the trial will be documented in the electronic case report form (e-CRF). In case of any protocol deviations, they will be limited to that specific patient. The investigator(s) will comprehensively document the deviation and its reason in the e-CRF. If a deviation pertains to inclusion/exclusion criteria, investigators must contact the clinical monitor to inform them by phone.

XI) Definition of Study End

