8. SUBJECT SELECTION AND WITHDRAWAL

I) Inclusion Criteria

1. Diagnosis of Ulcerative Colitis based on the European Crohn's and Colitis Organization criteria.
2. Patients aged 18 years or older.
3. Disease extension of at least left-sided (involvement >25 cm from the anal margin).
4. Moderate flare according to the Mayo Index (score ≥ 6 and ≤ 10).
5. No maintenance treatment or only 5-ASA oral and/or topical treatment.
6. Patient has the capacity to understand study requirements and provide informed consent.
7. Signed Informed Consent.

II) Exclusion Criteria

1. Previous or current treatment with thiopurines, calcineurin inhibitors, methotrexate, and/or biological agents.
2. Systemic corticosteroid use in the last 6 months (excluding topical oral corticosteroids).
3. Severe active or uncontrolled systemic infection, serious diseases, or medical conditions that may interfere with the patient's eligibility or treatment.
4. Uncontrolled diabetes mellitus or hypertension.
5. Psychiatric disorder or any other uncontrolled condition that contraindicates steroid treatment.
6. Pregnancy, lactation, or intention to become pregnant during the study period.
7. History of allergic reactions attributed to corticosteroids.

III) Withdrawal Criteria and Analysis

Premature termination of the trial will occur whenever the clinical trial is terminated before meeting the conditions outlined in the protocol.

Patients may be withdrawn from the study before reaching week 54 (end of follow-up) for any of the following reasons:

- **Patient Decision:** Patients are free to withdraw from the study at any time without any penalty or impact on their disease management or subsequent treatments.
- **Pregnancy.**
- **Serious Complications Due to Steroid Treatment.**
- **Lack of Early Clinical Response.**
- **Failure to Achieve Clinical and Endoscopic Remission, Steroid-Free at Week 8.**
- **Clinical Worsening and Need for Rescue Treatment at the Investigator's Discretion.**
- **Major Protocol Deviation.**

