A serious adverse reaction whose nature, severity, or outcome is inconsistent with the reference safety information. In this case, the product information (SmPC) will be used as the reference.

SAEs that meet the SUSAR criteria and are associated with blinded studies should be reported to Health Authorities with the open-label unblinding.

Adverse Events of Special Interest in this Study

Infections, events that lead to the discontinuation of the study treatment, and the development of diabetes mellitus or hypertension are considered of special interest.

Expected Adverse Reactions Not Clinically Significant in this Study

The following adverse reactions are commonly associated with the study medication in clinical practice. They will be recorded in the patient's medical history, but for reporting purposes, they will not be collected in the e-CRF unless, in the investigator's clinical judgment, they meet the severity criteria.

These include the occurrence of hirsutism, moon face, acne, insomnia, weight gain, buffalo hump, and stretch marks.

II) Methods and Schedule for Evaluation, Recording, and Analysis of Safety Parameters

Adverse events will be recorded from the administration of the study drug until the end of the patient's participation in the study, whether spontaneously reported by the patient or detected during study visits.

Follow-up of all ARs, SAEs, and SAREs will be conducted until resolution, irreversibility, or study completion, whichever occurs first.

All ARs, SAEs, SAREs must be documented in the patient's medical history and in the e-CRF, except for clinically insignificant ARs described above.

Any pregnancy occurring during the study and its outcome must be recorded and followed to rule out congenital anomalies or malformations. Information will be gathered on:

- Normal birth, spontaneous or therapeutic abortion (any congenital anomaly detected in the aborted fetus should be documented), stillbirth, congenital anomaly.
- Neonatal deaths within 30 days of birth.
- Infant death after 30 days if the investigator suspects it is related to in-utero exposure to the study medication.
- All infants born after fetal exposure must be followed during the first 12 months after delivery.

Any exacerbation of a pre-existing disease occurring after the start of the study treatment is also considered an adverse event.

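### A whole-study adverse event comparison can mix colitis failure with harm and rest on unequal observation time, and no early fixed-window table is planned

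*Combined protocol and SAP*

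**What the plan says.** - Section 7.I names the adverse event rate "and rate of severe adverse events (including hospitalizations) recorded throughout the study duration" among the secondary variables. "Rate" is not defined further.
- Section 11.II sets the period for each patient: "Adverse events will be recorded from the administration of the study drug until the end of the patient's participation in the study".
- Section 11.II also states: "Any exacerbation of a pre-existing disease occurring after the start of the study treatment is also considered an adverse event". Nothing there or elsewhere says whether a flare of the colitis under study is left out.
- Section 8.III: "Patients may be withdrawn from the study before reaching week 54 (end of follow-up) for any of the following reasons". The reasons include lack of early clinical response, failure at week 8, and worsening that needs rescue. Section 7.VII has a similar list, including "Lack of Clinical and Endoscopic Remission, Steroid-Free at Week 8".
- After an adverse event that stops the study drug, section 5.III has the participant followed to the end of the study. Section 11.IV has such a patient excluded from it.
- Section 12.I assigns chi-squared and t-tests to most secondary objectives. It gives no adverse event window, exposure-adjusted rate or time-to-first-event analysis. The 30-day rule for serious adverse events in section 11.II governs reporting, not analysis.

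**The concern.** The arms differ essentially by three days of intravenous methylprednisolone before the same 8-week oral course. The rest of the year is common background, apart from any difference in how the colitis behaves. Three things can then affect a comparison over the whole of participation.

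1. **Failure counted as harm.** If flares are logged as adverse events and the bolus works, the oral arm collects more of them. That hides bolus harm or looks like a safety benefit.
2. **Observation time that depends on outcome.** If patients who fail are withdrawn, the arm with more failures is watched for less time. If the bolus works, it then looks worse than it is.
3. **Dilution.** If the summary is patients with at least one event, background events later in the year shrink any early difference.

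These do not all run the same way, so an overall rate in either direction would be hard to interpret. The plan assesses early benefit at days 3 and 7 but has no matching early look at harm. Events that go unrecorded after a patient leaves cannot be recovered later.

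**Working it through.** **Inputs from the protocol.** Section 7.III: "20% in the control group (oral prednisone), a total of 148 patients are needed". Section 12 gives the expected bolus rate as 40%. Failure on the primary outcome is therefore 80% oral and 60% bolus. With 1:1 allocation there are 74 per arm. The planned end is week 54 (378 days), so the period after the 8-week course is 46 weeks.

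**The plan's own figure.** A one-sided 5% test of 20% v 40% with 80% power needs 64 per arm without continuity correction. Then 64/0.9 gives 72 per arm, 144 in total, within 3% of 148. With continuity correction it is 74 per arm, exactly 148 but with no dropout allowance. The sample size is not in question; it supplies only the 74 per arm.

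**Assumed, because the documents give no figure.** Early adverse event risk 20% oral v 35% bolus (or 20% in both arms for no harm); later risk 30% to 50%; share and timing of withdrawal; share of failures logged as a flare. Early and late risks are taken as independent, and the summary is patients with at least one event. Power is exact for the uncorrected two-sided 5% chi-squared test at 74 per arm, with no loss.

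**Dilution.** Total risk = 1 − (1 − early)(1 − L), so the difference is multiplied by (1 − L).
- No later events: 20% v 35%, 15 points, power 54.1%.
- L = 30%: 44.0% v 54.5%, 10.5 points, power 27.0%.
- L = 50%: 60.0% v 67.5%, 7.5 points, power 15.9%.

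**Unequal follow-up, no true harm.** Early risk is 20% in both arms and late risk 40% at constant hazard. A share f of failures leaves at fraction t of the late period: late risk = fail·f·(1 − 0.6^t) + (1 − fail·f)·0.40. Mean weeks observed = 8 + 46·(1 − fail·f·(1 − t)).
- t = 0.5, f = 0.5: 46.4% v 47.8%, spurious bolus excess 1.4 points; 44.8 v 47.1 weeks.
- t = 0.5, f = 1: 40.8% v 43.6%, 2.8 points; 35.6 v 40.2 weeks.
- t = 0, f = 0.5: 39.2% v 42.4%, 3.2 points; 35.6 v 40.2 weeks.
- t = 0, f = 1: 26.4% v 32.8%, 6.4 points; 17.2 v 26.4 weeks.
- Nobody leaves: 52.0% in both arms, 0 points.

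**Flares counted.** A share q of failures is logged as a flare event: total = 1 − (1 − early)(1 − fail·q).
- No harm: q = 0.25 gives 36.0% v 32.0% (−4.0 points); q = 0.5 gives 52.0% v 44.0% (−8.0 points).
- True 15-point excess: q = 0.25 gives 36.0% v 44.75% (+8.75, power 20%); q = 0.5 gives 52.0% v 54.5% (+2.5, power 7%). The loss is 6.25 or 12.5 points.

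**The effects interact.** A patient who leaves before flaring cannot log a flare. At q = 0.25 with no harm, the 4.0-point distortion falls to 2.0 if half of failures leave first, and to 0 if all do.

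**What a window would recover.** The taper of 60, 50, 40, 30, 20, 15, 10 and 5 mg is 8 × 7 = 56 days. Adding 30 days gives day 86 oral and 3 + 56 + 30 = day 89 bolus, so day 90 covers both. If the later risk L is spread evenly over the 378 days, background to day d = 1 − (1 − L)^(d/378). The 95% CI half-width is 1.96·√(p₁(1 − p₁)/74 + p₂(1 − p₂)/74).

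| Window | L | Background | Difference | Power | 95% CI |
|---|---|---|---|---|---|
| Day 30 | 30% | 2.8% | 14.6 | 50.1% | ±14.5 |
| Day 30 | 50% | 5.4% | 14.2 | 46.5% | ±14.8 |
| Day 90 | 30% | 8.1% | 13.8 | 43.0% | ±15.0 |
| Day 90 | 50% | 15.2% | 12.7 | 36.4% | ±15.5 |

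If a 30% background falls entirely before day 90, the day-90 figures are 10.5 points, 27.0% power and ±16.0. Day 30 is therefore the better window for an early excess.

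**The case against.** The plan has real safeguards. Section 11.I requires causality grading that weighs timing and match to known reactions, so related events could be shown apart from background. For serious events, the section 11.II reporting rule runs to 30 days after the last dose, without limit if related or medically important. Relapse, rescue, steroid dependency and surgery are separate variables in section 7.I, and need for hospitalization is a separate objective in section 6. A reader might infer that the trial could not separate flares from harm at all; these provisions do not support that reading. They do not remove the problem, because the comparison is not restricted to related events, grading is done open-label, and no rule keeps flares out of the count.

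The analysis itself is partly inferred. Section 7.I states a collection period, and chi-squared follows only from the general sentence in section 12.I. If "rate" means events per patient, equal later events leave the absolute excess unchanged, so dilution is conditional.

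The documents also do not say that bolus harm is mainly early. The special-interest events (infection, discontinuation, new diabetes or hypertension) are not tied to the first month, and a whole-study comparison by randomised arm is legitimate. That is why it should stay.

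Finally, planned follow-up is the same in both arms and withdrawal is permitted, not required. The midway-exit distortion of 1.4 to 2.8 points is small beside an interval of about ±16. The 80% v 60% failure includes patients who never reach endoscopic remission, which need not be an exacerbation. All of this stands and limits the claim.

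**Conclusion.** The concern holds in a limited form. Followed as written, the rules can put efficacy failures into the safety count and let observation time depend on outcome. If patients with at least one event are compared, later events also dilute an early difference. Under the assumed rates, the separate effects run from 0 to 6.4 points against the bolus (unequal follow-up), 4 to 12.5 points in its favour (flares), and a loss of 4.5 to 7.5 points from a 15-point early excess (dilution).

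A reader might go further and conclude that the plan conceals bolus harm, or that it is biased in a known direction. The documents support neither. They give no adverse event rates and no withdrawal timing, and the effects partly cancel. The matter concerns secondary safety comparisons, not the primary outcome. It is an improvement worth making before the data are seen, not a correction of an invalid analysis.

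**What to change.** In sections 7.I and 12:
- Keep the whole-study rate.
- Add a pre-specified table by randomised arm of patients with at least one adverse, serious or special-interest event by day 30 and by day 90 from the first steroid dose, not cut at rescue. Report the risk difference with its 95% CI as an estimate, and read day 30 first for an early excess.
- Put colitis exacerbations, and admissions for them, in a separate row.

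In section 11:
- Continue adverse event recording to at least day 90 after failure, rescue or an adverse event stop, unless consent is withdrawn.
- Align section 11.IV with section 5.III, so that patients stopped for an adverse event are followed to the end of the study.

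The cost is wording, one extra set of tables, event onset dates on the e-CRF, and brief day-30 and day-90 contacts for patients who leave early. Precision stays modest at about ±15 points, background events inside the windows still dilute somewhat, and late effects appear only in the whole-study table. The extra day-2 visit in the bolus arm and the steroid reactions kept out of the e-CRF are separate issues and not part of this change.

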An interim analysis will be conducted that will evaluate only the primary objective of the study (the proportion of patients who have achieved clinical and endoscopic remission, steroid-free at weeks 8 and 54, and without corticosteroid or rescue treatment). This analysis will be performed once 50% of the planned sample has completed the study. If the upper limit of the 95% confidence interval for the treatment efficacy in the experimental group is lower than initially expected (40%), or if the upper limit of the 95% confidence interval for the observed difference between the treatment groups for the primary endpoint is less than expected (20%), the study may be stopped for futility.

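### A single block size of 4 is printed in an open-label protocol that does not say who can see cumulative allocations; varying, undisclosed block sizes and an own-site view limit would be a cheap improvement

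*Combined protocol and SAP*

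**What the plan says.** Section 7, IV (Randomization and Blinding Techniques) sets the method. "Patients will be randomized (1:1) into each treatment arm via a computerized system provided by AEG-RedCap". The blocks and the first stratification factor follow: "Randomization will be performed in blocks of 4 and stratified by (1) whether the disease is newly diagnosed". The second factor is "whether the patient has received maintenance treatment with mesalazine at doses > 2 grams/day in the last three months". Two binary factors give four strata on paper. In practice there are probably three, since a newly diagnosed patient would hardly have been on maintenance mesalazine.

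The same section says: "This is an open-label study, meaning both the study subjects and investigators will be aware of the assigned treatment". Section 7, II confirms the setting: "This is a Phase IV, controlled, prospective, randomized, open, multicenter study". Site is not named as a stratification factor. The number of sites is not in the text available; the list is in Annex 1.

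The documents do not mention block sizes that vary, withholding the block size from investigators, or who can view the running list of allocations within a stratum.

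Two other passages bear on the consequences. Section 7, IX has the endoscopies assessed blind by the endoscopists. Section 12, I compares the primary endpoint between arms with an unadjusted Chi-squared test.

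**The concern.** Prediction within permuted blocks needs two things: a known block size and sight of the earlier allocations in the block. The protocol supplies the first to every investigator. Because the trial is open, each site also has the second for its own patients. With blocks of 4 in a 1:1 trial, the last allocation is fixed by the first three, and the third is fixed whenever the first two match.

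A recruiter who knows the next assignment can hold back or bring forward a candidate according to prognosis. There is room for judgement at entry: Section 8 admits Mayo scores from 6 to 10 and excludes conditions that may interfere with eligibility or treatment. The planned unadjusted test would not correct for such selection. Blinded endoscopy would not prevent it either, because it happens before any outcome is read. In an open trial, concealment of the next allocation is the main protection against selective enrolment, so how far it can be breached is worth working out.

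**Working it through.** **Inputs.** From Section 7: block size 4, ratio 1:1, 148 patients (74 per arm), control success 20%, one-sided 5% level. From Section 12: expected experimental success 40%. Assumptions, not in the documents: a 10-point difference in success chance between candidates a recruiter might choose; equal site sizes; an informed site with 20% of recruitment; 37 patients per stratum (148/4) for the simulation.

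**The plan's own figure.** The protocol gives no predictability figure. Its sample size, for 20% against 40%, is close to the uncorrected one-sided formula: (1.645·√(2·0.3·0.7) + 0.842·√(0.2·0.8 + 0.4·0.6))² / 0.2² = 63.9, so 64 per arm; 64/0.9 gives 72 per arm, or 144 in total against 148. The block result below does not depend on this number.

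**1. Full view of a stratum, blocks of 4.** Six arrangements are equally likely. AABB and BBAA each fix two allocations in advance; the other four each fix one.
- Certain: (2·2 + 4·1)/(6·4) = 8/24 = 1/3, about 49 of 148.
- Best guess correct, averaged over the four positions: (1/2 + 2/3 + 2/3 + 1)/4 = 70.8%, against 50% by chance.

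**2. Own-site view only.** Let a site contribute a share q of the stratum, and grant it knowledge of where each block starts. An allocation is certain only if the two earlier patients in that block who went to the opposite arm were both its own, which has probability q². The certain share is therefore q²/3:
- 2 equal sites: 0.25/3 = 8.3%
- 5 sites: 0.04/3 = 1.3%
- 10 sites: 0.01/3 = 0.3%

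Simulation gives the same values (8.2%, 1.3%, 0.3%). Granting the block boundaries is generous, because a site that cannot see other sites' enrolments would not normally know them.

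**3. Bias if recruiters act only when certain.** Bias = share certain × difference between candidates. Rejection rates under the null are exact binomial calculations with 74 per arm, a one-sided 5% test and mean success rates of 20–30%.

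| Scenario | Bias (points) | Rejection under the null |
|---|---|---|
| Every recruiter has full view, fixed blocks of 4 | 10 × 1/3 = 3.3 | 11–13% |
| One informed site with 20% of recruitment | 3.3 × 0.20 = 0.7 | about 6% |
| Every recruiter has full view, random sizes 4, 6, 8 | 10 × 0.02 = 0.2 | about 5% |

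**4. Bias if recruiters act on their best guess.** Bias = 10 × (2 × accuracy − 1). With every recruiter in full view:
- fixed blocks of 4: 10 × (2·0.708 − 1) = 4.2 points, rejection 14–16%
- sizes 4, 6, 8: 10 × (2·0.68 − 1) = 3.6 points, rejection 12–14%

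**5. What varying the size buys.** The simulated observer sees the whole stratum, knows the set of possible sizes but not their order, and follows 37 patients. The fixed-block row is the complete-block value from step 1; over 37 patients it simulates as about 32% and 70%.

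| Block sizes | Certain | Best guess correct |
|---|---|---|
| 4 only | 33% | 71% |
| 4 and 6 | about 6% | 69% |
| 4, 6 and 8 | about 2% | 68% |

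Varying the size removes nearly all certainty but little of the guessing advantage.

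**The case against.** A reader might infer that, because the trial is open, every past allocation is visible and every investigator can foresee one allocation in three. The documents do not support that. Open-label treatment tells a site about its own patients. Allocation runs through a computerised system, the strata are shared across sites, and nothing says that a site can see the others' assignments. One in three is therefore the rate for someone with a whole-stratum view, not for a typical recruiter. This part of the objection stands.

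The 3.3-point bias is equally conditional. It needs full view at every site and action on every certain slot. A single informed site, such as a coordinating centre, can steer only the patients it recruits. The 10-point gap between candidates has no source in the documents; the bias scales in proportion to it.

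Timing also limits exploitation. Recruiting 148 patients in 104 weeks is about 1.4 a week over all sites, or one per stratum about every two weeks with three equal strata. Holding back a patient in a moderate flare is difficult, and another site's enrolment may use up the awaited slot.

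Finally, endoscopic reading is blinded, so it would be wrong to describe the whole primary endpoint as resting on unblinded ratings. The clinical and rescue components are not described as blinded. That distinction concerns outcome assessment and does not answer selection at entry.

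What survives is narrower: the block size is fixed and printed, and the access rule that would make this harmless is not written down.

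**Conclusion.** The point holds as a conditional weakness in allocation concealment. With a full view of a stratum, one allocation in three is certain and 71% can be guessed. With an own-site view the certain share falls to about 8% for two equal sites and about 1% for five. Which case applies cannot be settled from the documents.

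The 11–13% rejection rate is an all-sites worst case under an assumed 10-point prognostic gap and should not be read as the trial's type I error. With one informed site recruiting an assumed 20% of patients, the same reasoning gives about 0.7 points and 6%. Nothing in the documents shows that any site has foreknowledge or has used it. This is an optional improvement, worth making because it costs so little.

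**What to change.** In Section 7, IV, replace the fixed block size with randomly permuted blocks of varying size and keep both stratification factors. Hold the sizes in a restricted randomisation file that investigators do not see, and do not print them in the protocol. Add a sentence that each site's view of allocations in the randomisation system is limited to its own patients, and name the roles that may see more.

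Both parts are needed. Varying the size deals with certainty, while the view limit deals with the guessing advantage that remains. If the system already restricts the view, stating so would resolve most of the concern.

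The cost is a new allocation table, a few words of protocol text and a system permission. No patients or visits are added. With blocks of up to 8, the within-stratum imbalance at any moment can reach 4 patients instead of 2. If enrolment has already run under blocks of 4, the useful step is to report who had access to the sequence.
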